In the event of an adverse event, subjects will have ready access to the study coordinator and principal investigator for the appropriate intervention. All adverse events will be reported in accordance with existing guidelines of IRBs and the FDA.

D.11. Subject Confidentiality

Assigning each subject a study number and acrostic will protect subject confidentiality. This number will be the only identification used in any communication or report. Accordingly, subject confidentiality and anonymity will be protected at all times according to institutional policies, IRB and HIPAA regulations.

E. Ethics

E.1. Independent Ethics Committee/Institutional Review Board

The investigator must submit this protocol, informed parent consent form, and subject information to an Institutional Review Board (IRB). Prior to the beginning of the study, the investigator must obtain written IRB approval of the protocol, consent form, and subject information. The investigator may not initiate the study until IRB approval has been obtained. The Investigator has the responsibility to notify the IRB if the study is either amended or terminated. Emergency changes to protect the life of the subject do not require prior approval, but must be reported to the IRB immediately.

Written informed consent must be obtained from the participant's legal guardian prior to their participation in the study after the IRB approval of the study protocol and parent consent form.

E.2. Ethical Conduct of the Study

The study will be conducted under the following conditions:

1. Declaration of Helsinki
2. ICH Guidelines for Good Clinical Practice (GCP)
3. GCP/International Conference on Harmonization (ICH) guidelines

E.3. Subject Information, Confidentiality and Consent

All subject information, medical records, and laboratory data will be kept confidential. Information and data may be discussed, analyzed, and reported. However, ID numbers will identify the subject on the case report forms and the subject's identity will be kept confidential.

Once the entire study has been explained and understood, the subject's legal guardian will sign and date the IRB approved informed parent consent form.

F. Study Administration Structure

F.1. Investigator Responsibilities

F.1.1. Investigator Agreement

The investigator must sign FDA Form 1572, the Investigator Agreement, certifying that he/she will conduct the investigation in accordance with U.S. Federal Investigational New Drug regulations (21 CFR 312). The investigator is responsible for ensuring that the investigation is conducted in accordance with the investigational plan, and all IND and relevant FDA regulations for the protection of subjects' rights, safety, and welfare while under the investigator's care.

The investigator must notify the sponsor and the reviewing IRB of any deviation from the investigational plan to protect the life or physical well-being of a subject in an emergency. This notice shall be given as soon as possible but no later than five working days after such deviation occurred.

F.1.2. Institutional Review Board (IRB) Approval

Under the Code of Federal Regulations, 21 CFR §50, an appropriate Institutional Review Board, or like assembly, must review this protocol, the Informed Consent Form, and any other supporting study documents which impact subject safety, prior to study initiation.

The Institutional Review Board must review the protocol, and any amendments or revisions, and the Informed Consent Form at least annually over the course of this study. The study cannot continue until the IRB has given written renewal approval, signed by the board chairperson or authorized personnel, and the sponsor has on file a copy of the renewal approval letter and the approved Informed Consent Form.

F.1.3. Informed Consent

The investigator is required to obtain in writing a legally effective informed consent from the study subject's parents/guardian prior to the subject's participation in the investigation. No human being as a subject can participate in this study without such consent. The Informed Consent Form must be approved by the site's Institutional Review Board (IRB). The investigator shall seek such consent only under circumstances that provide the prospective subject's guardian sufficient opportunity to consider whether or not to participate and that minimize the possibility of coercion or undue influence. The information that is given to the subject's parents/guardian shall be in language understandable to the subject's parents/guardian. Sufficient time must be available for the subject's guardian to have all questions answered.

In addition to the written explanation in the Informed Consent Form, a verbal explanation will be given by the investigator or his/her designee. The investigator or his/her designee will further explain the reason for the study, the risk to the subject of participating in the study as well as the potential benefits and alternative treatments the subject would receive should he/she choose not to participate in the study. The consent process will also be documented in the subject's research chart.

F.1.4. Records Maintenance

F.1.4.a. Administrative and Regulatory Files

The administrative and regulatory files include the following:

- IRB membership list / address;
- Original application to IRB, original approval letter - signed and dated;
- Additional submissions with amendments or changes and all approval letters
- Informed Consent original approval letter, signed and dated;
- All subsequent renewal application, and renewal approvals;
- Reports, at least annually, to the IRB.

F.1.4.b. Investigator Information

Including but not limited to the following:

- Investigator Curriculum Vitae;
- FDA Form 1571
- FDA Form 1572 - Investigator Agreement(s) - signed / dated;
- Monitoring records - including a sign-in log listing date, duration, and purpose of visit

F.1.4.c. Documentation of Adverse Events, Protocol Deviation, Failure to Obtain Informed Consent, Subject Withdrawal

Documentation regarding any of the following:

- Adverse events or drug complications;
- Deviations from the protocol;
- Failure to obtain informed consent prior to subject participation;
- Subject withdrawal from the study.

F.1.4.d. Data Corrections

All corrections to the data, either on a case report form or the medical record, will be:

- lined through so that the original entry can still be viewed
- initialed and dated by the individual making the correction
- corrected legibly
- reason for the correction will be noted only in the event that it is a “subjective” change (e.g., change from mild to moderate); otherwise changes should be supported by source document

Please note that whiteout or other corrective fluids will not be used at any time on the forms.

SECTION 2

Literature Cited in Research Plan

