*Principal investigator

** Sponsor

SECTION 1

1. Introductory Statement

Title: Autologous Cardiac Stem Cell Injection in Patients with Hypoplastic Left Heart Syndrome: An Open Label Pilot Study. (CHILD Study)

Sponsor: [name].
Interdisciplinary Stem Cell Institute
University of Miami Miller School of Medicine,
Division of Cardiology, Miami, Florida

Cell Manufacturing Center:
Interdisciplinary Stem Cell Institute
Clinical Research Cell Manufacturing (CRCMP) Program
University of Miami Miller School of Medicine
[name]
[name]

Test Agent: Autologous c-kit-positive cells (c-kit⁺ cells)

Population: Male or female neonates diagnosed with hypoplastic left heart syndrome (HLHS) undergoing Stage I Norwood operation.

Sample Size: A total of 32 subjects will be enrolled for this pilot study in a staged enrollment.

Treatment: All subjects with the diagnosis of hypoplastic left heart syndrome (HLHS) undergo a palliative reconstructive surgery performed in the first two weeks of life, termed the Norwood procedure. The Norwood procedure involves reconstruction of the aortic arch, resection of the atrial septum, and establishment of pulmonary blood flow through either a modified Blalock-Taussig shunt (mBTS) (a Gore-Tex tube from the innominate artery to the right pulmonary artery) or a Sano shunt (a Gore-Tex tube from the right ventricle to the right pulmonary artery). To initiate cardiopulmonary bypass for this surgery, the right atrial appendage is cannulated. Typically, the appendage is excised and discarded during this step. However, in our study, this excised right atrial appendage will be harvested and c-kit⁺ cells will be isolated. The process and manufacturing of the c-kit⁺ cells will be exactly as specified in the TAC-HFT II Study (IND# 14647, NCT00768066). TAC-HFT II was a Phase I/II, Randomized, Placebo-Controlled Study of the Safety and Efficacy of Transendocardial Injection of Autologous Human Cells (Mesenchymal or the combination of MSC and ckit+ in Patients with Chronic Ischemic Left Ventricular Dysfunction and Heart Failure Secondary to Myocardial Infarction trial of University of Miami under IND #14647. The patients will then proceed with the typical postoperative care. The second stage in the palliation of HLHS is a scheduled bidirectional cavopulmonary anastomosis, BDCPA) operation that

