We plan to enroll thirty-two patients with HLHS in a two staged enrollment process. In this study, a maximum of 21 patients will receive intramyocardial injection of c-kit⁺ cells and 11 standard of care control patients with no injection. The enrollment of the patients will occur in two staged groups: Group A and Group B. Initially in Group A, 10 consecutive HLHS patients will be enrolled in the c-kit⁺ cell treatment arm to determine feasibility and safety. Six months after the last patient is enrolled in Group A, the DSMB will conduct a review of all Group A patients in order to determine whether the methodology is feasible and safe, including the harvesting, processing, and administering of the c-kit⁺ cells. Thereafter, Group B will enroll a total of 22 HLHS patients which will be randomized, double-blinded to the treatment and standard of care control arms in a 1:1 ratio, respectively, in order to have 11 c-kit⁺ cell-treated patients and 11 control patients. Randomization will occur post-Norwood operation upon receipt of viable tissue sample at University of Miami Clinical Research Cell Manufacturing Program (CRCMP). The rationale underlying this two-staged enrollment is to initially test the feasibility and safety of this methodology of obtaining the c-kit⁺ cells from the right atrial appendage with the Group A patients. The second Group B patients may provide the required numbers to potentially validate the efficacy of the trial. Eventually, a Phase II trial will provide the necessary numbers to provide an accurate assessment of efficacy of the c-kit⁺ cells in HLHS patients.

B.1.2. Sample Size

Twenty-one (21) subjects will be enrolled in the treatment group and eleven (11) in the standard of care control group. The 10 Group A subjects are part of an open-label safety and feasibility analysis. The 22 Group B subjects will be randomized 1:1 to cell treatment and control to detect a difference of 6 RVEF units, given a standard deviation of 4, 89% power and type 1 error of 0.05. Twenty patients are needed with 10% added for possible lost to follow-up.

B.1.3. Dosage and Administration

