The treated HLHS patients will receive up to 12,500 cells/kg. The terminology “up to” a certain dose indicates that if the number of the c-kit⁺ cells is not sufficiently attainable from the cardiac specimen to the specified dose then the achievable dose will be delivered. A secondary analysis of subjects who achieve ≥80% of the assigned dose will be performed as part of the overall analysis plan. The decision to weight-adjust the dose of cells was made based on preclinical studies. The cells will be delivered through 6-10 intramyocardial injections of approximately 100uL per injection for total volume of 0.6 mL

B.1.4. Premature Withdrawal

For subjects withdrawn after receiving study product injection, all efforts will be made to encourage return for all assessments through the end of the study period, so that safety can continue to be monitored.

Because the data from the proposed trial may be used to design future phases of clinical trials, we put a high priority on collecting data that is complete and accurately describes the safety and efficacy of the intervention as described. Therefore, the goal is to have final MRI and other efficacy endpoint measurements on at least 20 Group B subjects during the randomized portion of trial. As such, Group B study treatment subjects who do not undergo the stem cell injection or do not get the Stage II BDCPA operation can diminish the goal sample size of 20. A maximum of six additional subjects can be randomized to replace this potential loss to achieve the target sample size of 20 evaluable subjects.

B.2. Criteria for Subject Enrollment

B.2.1. Inclusion Criteria

For inclusion in the study, subjects must meet all of the inclusion criteria:

1. Subjects with hypoplastic left heart syndrome (all types) requiring Stage I Norwood operation.

B.2.2. Exclusion Criteria

Candidates will be excluded from the study if any of the following conditions are met:

1. Subjects undergoing the Stage I Norwood operation who do not have HLHS.
2. Subjects requiring mechanical circulatory support immediately prior to Stage II BDCPA operation (within 5 days).

3. Parent or guardian unwilling or unable to comply with necessary follow-up(s).
4. Mother is serum positive for HIV 1/2, hepatitis BsAg or viremic hepatitis C and *Treponema pallidum*.
5. Subjects who are unsuitable for inclusion in the study in the opinion of the investigator(s).

B.3 Sequence of Measurements and Evaluation

B.3.1. Subject Introduction and Informed Consent

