1. Student t-test will be used to assess the difference between the treatments in the change from baseline for continuous outcomes; also, analysis of covariance (ANCOVA) with adjustment for baseline values will be used to assess treatment effect.
2. Wilcoxon rank sum test will be used to assess the difference in treatment effect in the change from baseline for continuous outcomes if normality assumption does not hold.
3. Chi-square test or Fisher's exact test will be used to assess difference between treatments in incidence of categorical outcomes.
4. Logistic regression with baseline covariates will be used to assess treatment effect for categorical outcomes with adjustment for baseline covariates if appropriate.
5. No adjustment will be made for multiple comparisons.

C.6. Determination of Sample Size

A total of twenty-two subjects will be randomized to two groups (eleven control and eleven treated). In our statistical plan we have allowed for a 10% attrition rate, with one subject per group for the bioactivity analysis.

A sample of 20 participants (10 in the treatment group and 10 in the control) provides 89% power with an alpha of 0.05 to detect a 6 unit change in RVEF (with a SD of 4 units) between the stage II operation (baseline) and 12 months later as measured by cMRI

We performed a power analysis based on our pilot study and the PERSEUS trial published in the administration of cardiosphere derived cells in HLHS patients. The sample size for comparing means from two independent samples of a continuous variable is as follows:

$$n_C = \frac{2 * (Z_{1-\alpha/2} + Z_{1-\beta})^2 \sigma^2}{\delta^2}$$

In a 1:1 randomization, $n_A = n_C$, where n_A = number in the active groups and n_C = number in the control group $\delta = \mu_1 - \mu_2$ (difference of 2 means) and σ^2 is common variance. Total sample size is $2n_C$.

$Z_{1-\alpha/2}$ for an α of .05 for a 2-sided test is 1.96, $Z_{1-\beta}$ for power of .89 is 1.21. The primary analysis will consist of one comparison – cKit versus control. We assume that will have a 6 unit change in RVEF with a SD of 4 units based on data from the PERSEUS trial.¹

Analyses of bioactivity will be exploratory in nature in order to aid in selection of dosage, endpoints, time points, and sample size determination for subsequent larger trials.

C.7. Heart Tissue Analysis

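### The stated sample size of 32 omits the six replacements that B.1.4 allows (maximum 38, Group B 28), and the replacement trigger names only cell-arm children

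*Combined protocol and SAP*

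**What the plan says.** Section 1 (Sample Size) gives the total without qualification: "A total of 32 subjects will be enrolled for this pilot study in a staged enrollment". B.1.1 opens with "We plan to enroll thirty-two patients with HLHS in a two staged enrollment process" and breaks this into 10 Group A children, all assigned to cells, and 22 Group B children randomized 1:1. It adds that "a maximum of 21 patients will receive intramyocardial injection", with 11 controls. B.1.2 repeats 21 and 11, and explains the 22 as 20 needed plus 10% for loss to follow-up. C.6 also gives 22 randomized, and says: "In our statistical plan we have allowed for a 10% attrition rate, with one subject per group for the bioactivity analysis".

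B.1.4 (Premature Withdrawal) sets a goal of final MRI and other efficacy measurements on at least 20 Group B children. It names one source of shortfall: "Group B study treatment subjects who do not undergo the stem cell injection or do not get the Stage II BDCPA operation". The remedy follows: "A maximum of six additional subjects can be randomized to replace this potential loss to achieve the target sample size of 20 evaluable subjects". B.1.4 does not say how the additional children are allocated.

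C.2 defines the Efficacy Analysis Set (EAS) as all randomized subjects, analysed in the arm to which they were assigned.

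**The concern.** Two things do not fit together.

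First, a reader of the synopsis, the design section or either sample-size section would take 32 as the number of infants in the trial. The replacement rule permits more, and only B.1.4 says so. An IRB or DSMB working from the headline figure would be approving or monitoring against the wrong ceiling. The arm sizes of 11 and 11 also cease to be correct once the rule is used.

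Second, the goal covers Group B as a whole, but the trigger is written for study-treatment children. Randomization follows the Norwood operation, and Stage II comes at 4 to 6 months of age, so children in either arm can drop out in between. A control child who does not reach Stage II reduces the evaluable number just as a cell-arm child does, yet no replacement is provided. The rule can therefore fail to deliver the 20 it was written to protect.

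**Working it through.** **Inputs.** Group A 10 (B.1.1). Group B 22, as 11 and 11 (B.1.1, C.6). Evaluable target 20, with 10% added (B.1.2, C.6). Replacement cap 6 (B.1.4). Difference 6 RVEF units, SD 4, two-sided alpha 0.05, power 89% (B.1.2, C.6).

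**The plan's own figures reproduce.**
- C.6 formula: 2 × (1.96 + 1.21)² × 4² / 6² = 8.93 per arm. The plan uses 10.
- Power at 10 per arm, two-sample t-test: noncentrality 6 / (4 × √(1/10 + 1/10)) = 3.354 on 18 df, giving 88.7%. This matches the stated 89%.
- Loss allowance: 20 × 1.10 = 22.
- Total: 10 + 22 = 32.

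**With B.1.4 included.**
- Group B: 22 + 6 = 28.
- Total: 10 + 28 = 38.
- Loss that still leaves 20 evaluable: (22 − 20)/22 = 2/22 = 9.1% without replacement; (28 − 20)/28 = 8/28 = 28.6% with all six used.

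The 38 counts Group A plus randomized Group B. Consent comes before the Norwood operation, and randomization waits for viable tissue, so the number consented could be larger still.

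**How the target can be missed.** As an illustration, suppose three controls never reach Stage II and one injected child is lost to follow-up. None of these four meets the trigger as written. The evaluable set is 11 − 1 = 10 cells and 11 − 3 = 8 controls, 18 in all, although six replacements are unused. Noncentrality is 6 / (4 × √(1/10 + 1/8)) = 3.162 on 16 df, and power is 84.3% instead of 88.7%.

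**Does the maximum of 21 injected survive the present rule?** Both triggers describe children who were not injected. If k such children are replaced, and every replacement goes to the cell arm, the number injected is at most 10 + (11 − k) + k = 21. The cap holds.

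**The case against.** The strongest reply is that nothing is miscalculated. The figures 32, 22 and 89% all reproduce, B.1.4 states the cap openly in the same protocol, B.1.1 describes 32 as a plan, and the bioactivity analyses are exploratory. On this view only a cross-reference is missing. The first part stands: there is no power error and nothing is hidden. But Section 1 presents 32 as the total to be enrolled, and that is wrong whenever the protocol's own rule is used.

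It can also be said that B.1.4 never limits replacement to the cell arm and sets its goal for Group B as a whole. That is fair; the text does not say so expressly. Still, the only loss it describes is among study-treatment subjects, and that is the loss being replaced. At best, the position of controls is unclear.

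A reader might infer several stronger points that the documents do not support:

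- *That more than 21 children could be injected.* Not under the rule as written, as shown in the working.
- *That the plan expects 6/22 = 27% loss and so contradicts its 10%.* Six is a contingency cap. The 10% is for loss to follow-up; B.1.4 is for children who never receive the injection or Stage II. The two need not be equal.
- *That the evaluable split would become 8 against 14.* This needs six cell-arm losses, no other losses, all six replacements used and 1:1 allocation. Six losses from 22 leave 16, so four replacements reach the target of 20 and the rule's purpose is met. Even at 8 against 14, power would be 89.6%.
- *That replaced children drop out of the intention-to-treat set.* C.2 already keeps every randomized child in the EAS as assigned.

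**Conclusion.** The point holds as an inconsistency in the enrolment ceiling and a gap in the replacement rule. The permitted maximum is 38 rather than 32 in all, and 28 rather than 22 randomized. The loss compatible with 20 evaluable children is 28.6% with replacements and 9.1% without. As written, control children who do not reach Stage II have no replacement. In the 10 against 8 illustration this takes power to about 84%.

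The ceiling follows directly from the protocol's numbers. The power figures rest on its assumed difference of 6 and SD of 4, and the loss pattern in the illustration is an assumption, because the documents give no expected loss before Stage II by arm. The planned power of 89% at 10 per arm is not in question.

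**What to change.** 1. In Section 1, B.1.1, B.1.2 and C.6, state the sample size as 32, up to 38 with B.1.4 replacements (Group B 22, up to 28; 11 per arm before replacement).
2. In B.1.2 and C.6, say that the 10% covers loss to follow-up and that B.1.4 covers children without the Stage II operation or, in the cell arm, without the injection.
3. In B.1.4, trigger replacement on no Stage II operation in either arm, plus no injection in the cell arm. Allocate replacements 1:1 from the same randomization sequence until 20 are evaluable or six have been used.
4. Do not trigger on death, loss or a missed MRI after treatment. That would select on post-treatment outcome and could take the number injected above 21.
5. Keep the maximum of 21 injected and say how it binds. Once control losses also trigger replacement, a 1:1 draw could put a child in the cell arm when all 11 there have been injected, giving 10 + 12 = 22. The handling of such a draw must be fixed before any replacement is made.

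C.2 needs no change.

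Cost: items 1 and 2 are wording. Items 3 to 5 amend the replacement rule but allow no child beyond the six already permitted. The declared maximum enrolment becomes larger, and some of the six may be spent on control losses, leaving fewer for the cell arm.
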